#### **4.4.6 Suspension or Termination of the Study**

The study may be suspended or prematurely terminated by the NIDCR if reasonable cause exists, as determined by the PI, the NIDCR program official or medical monitor, the IRB, or the DSMB. Circumstances that may warrant suspension or termination include, but are not limited to, the following:

- Determination of unexpected, significant, or unacceptable risk to participants.
- Insufficient adherence to protocol requirements.
- Data that are insufficient and/or not evaluable.

If the study is prematurely suspended or terminated, the PI will provide written notification to the investigators, the NIDCR program official, the IRB, and the DSMB.

### **5 STUDY INVESTIGATIONAL PRODUCT AND PLACEBO**

The Investigators consulted with the FDA to determine whether this protocol should be conducted under an IND. The FDA determined that this clinical trial meets the exemption requirements for an IND. An overview of the investigational product and placebo are provided below; further details are available in the Manual of Procedures (MOP).

#### **5.1 Investigational Product**

The investigational product is propranolol hydrochloride extended-release capsules, an approved drug for the treatment of hypertension, angina pectoris due to coronary atherosclerosis, migraine, and hypertrophic subaortic stenosis. The package insert for propranolol hydrochloride extended-release is provided in Appendix B. Propranolol hydrochloride extended-release is a nonselective  $\beta$ -adrenergic receptor-blocking agent. The extended-release formula provides a sustained release of propranolol hydrochloride.

##### **5.1.1 Acquisition**

Propranolol hydrochloride extended-release 60 mg capsules will be acquired from a compounding pharmacy and shipped to the research pharmacy at each clinical site. The research pharmacies will dispense the drug.

##### **5.1.2 Formulation, Packaging, and Labeling**

The propranolol hydrochloride extended-release capsules will be over-encapsulated by the compounding pharmacy to have the same appearance as the placebo. Neither the study personnel nor the study participants will be able to differentiate the study drug from the placebo by appearance alone.

The research pharmacy will label and dispense the 60 mg capsules in tight, light-resistant containers. The containers will be labeled with the following information:

- Name and address of the dispensing pharmacy
- Protocol number
- Name of the drug labeled as “propranolol hydrochloride extended-release or placebo” to protect the blinding
- Strength of the drug (60 mg propranolol hydrochloride extended-release or placebo) and number of capsules dispensed
- Name of the prescribing clinician
- Instructions for use
- Participant name and medical record number
- Date dispensed
- The following statement: “Limited by Federal Law to Investigational Use Only”

### **5.1.3 Product Storage and Stability**

Propranolol hydrochloride extended-release capsules will be shipped and stored according to United States Pharmacopeial Convention (USP) Controlled Room Temperature guidelines and protected from light, moisture, freezing, and excessive heat.

## **5.2 Dosage and Administration of Investigational Product**

Propranolol hydrochloride extended-release 60 mg capsules will be dispensed at Visits 1, 2, 3, and 4 as described below:

- Visit 1 (beginning of the 1-week titration): 1 capsule per day in the evening
- Visit 2 (beginning of the first 4 weeks of maintenance): 2 capsules per day, one in the morning and one in the evening
- Visit 3 (beginning of the last 4 weeks of maintenance): 2 capsules per day, one in the morning and one in the evening
- Visit 4 (beginning of the 1-week tapering): 1 capsule per day in the evening

## **5.3 Modification of Dosage of Investigational Product**

If a participant cannot tolerate the scheduled titration or maintenance dosage, they will remain in the study at either a lower, tolerated dosage or without taking study medication. These events will be recorded as protocol deviations.

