### **4.4.3 Unblinding Procedures**

Unblinding before the study is completed will occur only if a participant's well-being is threatened and is necessary to protect the participant. Except in extreme medical emergencies, before the treatment assignment for a participant is unblinded, the investigator must confer with the National Institute of Dental and Craniofacial Research (NIDCR) medical monitor and the site cardiologist as necessary. For extreme medical emergencies that occur during business hours, the clinical site investigator will contact the DCC to determine the participant's treatment assignment. For extreme medical emergencies that occur outside of business hours, medical personnel will contact the site pharmacy to determine the participant's treatment assignment. An event is considered an extreme medical emergency when appropriate medical management of

---

the participant necessitates knowledge of treatment assignment. Study participants will be provided with instructions and contact information for emergency situations. The emergency unblinding will be recorded and reported to the PI and to the NIDCR medical monitor as soon as possible. A full account of the event will be recorded, including the date and time of the emergency, the reason for unblinding, and the names of the medical monitor and others who were notified of the emergency. The unblinding will be reported to the DSMB and the IRBs according to reporting guidelines for those boards.

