#### **4.4.4 Reasons for Participant Withdrawal**

Participants are free to withdraw from participation in the study at any time, and the investigator may withdraw a participant for any of the following reasons:

- Withdrawal of consent.
- Does not meet criteria for randomization.
- Pregnancy.
- Continued participation deemed to be not in the participant's best interest.
- Investigator discretion.

Participants requiring significant surgery will be withdrawn from the protocol. Investigators will use discretion in making this determination. Participants withdrawn after randomization will not be replaced. If a participant does not return for a scheduled visit, every effort should be made to contact the participant and document the outcome. If the participant withdraws consent, no further evaluations will be performed, and no attempts will be made to collect additional data.

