#### **4.4.5 Handling of Withdrawals and Discontinuation**

Participants who withdraw from the study voluntarily or are withdrawn by an investigator will be discontinued from the study. Study staff will complete a study disposition form in the electronic data capture (EDC) system, indicating the reason for discontinuation. If the participant is on study drug at discontinuation, the investigators, in consultation with the site cardiologist, will decide the following: (1) the need for tapering of the investigational drug, (2) whether tapering will be conducted by the investigator prior to discontinuation or by a referring practitioner after discontinuation, and (3) whether unblinding of the treatment assignment will be required. If unblinding is required, the investigator will follow the unblinding procedures described in Section 4.4.3.

Any participant with an AE that is ongoing at the time of discontinuation will be followed until the event returns to baseline, resolves, or stabilizes. If the AE does not meet these outcomes within 30 days after discontinuation or the end of the study, the participant will be referred to an appropriate practitioner for continued care.

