## **5.4 Placebo**

The placebo, which will be manufactured for this study, will be acquired, packaged, labeled, dispensed, and administered in the same manner as described above for the active drug.

---

Ingredients will be a microcrystalline cellulose filler and a gelatin capsule. Storage requirements for the placebo are the same as for the active drug.

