### **5.8 Protocol Deviations Related to the Use of Investigational Product and Concomitant Therapies**

The following protocol deviations related to the use of investigational product and concomitant therapies will be considered major protocol deviations and reported on a case report form in the EDC system.

- Participant is unable to reach the maintenance dosage of the study drug or placebo or is unable to remain on the maintenance dosage.
- Initiation of opioid medications.
- Initiation of TMJ surgical treatment (including TMJ arthrocentesis).
- Initiation of therapeutic injections for the management of pain.
- Initiation of occlusal splint therapy.
- Initiation of any of the following nonpharmacological therapies: acupuncture, biofeedback, and/or TENS.
- Initiation after Visit 1 and usage of short-acting, non-prescription analgesics (e.g., NSAIDs, aspirin, and/or acetaminophen) for pain that exceeds the definition of episodic use as described in Section 5.7.1.

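### Section 5.3 lets a participant stop 120 mg/day of study medication and stay in the study, and neither of the protocol's taper provisions reaches that stop (minor safety gap)

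*Protocol*

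**What the plan says.** - **Dosing (Protocol 5.2; SAP 2.4).** Titration is one 60 mg capsule daily and maintenance is two. The scheduled step-down is at "Visit 4 (beginning of the 1-week tapering): 1 capsule per day in the evening".
- **Intolerance (Protocol 5.3).** For a participant who cannot tolerate titration or maintenance, "they will remain in the study at either a lower, tolerated dosage or without taking study medication". The event is recorded as a protocol deviation.
- **Deviations (Protocol 5.8).** The list of major deviations includes "Participant is unable to reach the maintenance dosage of the study drug or placebo or is unable to remain on the maintenance dosage". It does not mention how the drug is stopped.
- **Leaving the study (Protocol 4.4.5).** "If the participant is on study drug at discontinuation, the investigators, in consultation with the site cardiologist, will decide the following": whether a taper is needed, who conducts it, and whether to unblind. The Early Termination Visit (6.5), which repeats the Visit 4 procedures, is likewise for participants discontinued before completion.
- **Other sources.** Section 5 describes itself as an overview and refers to the MOP for detail. Appendix B is the propranolol label.

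**The concern.** The protocol provides for the end of treatment in two situations. Completers step down for a week, and participants who leave while on drug get a decision made with the site cardiologist. A participant who stops under 5.3 but stays in the study gets neither in the protocol text, although the dose being left is the same. If that participant leaves later, 4.4.5 still does not apply, because they are no longer on study drug.

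What is at stake is safety on withdrawal of a beta-blocker. The label's angina warning reports worsened angina, and in some cases infarction, after abrupt discontinuance. It suggests caution in patients at risk of unrecognized coronary disease who take the drug for other reasons. The protocol's own risk section (2.3.1) does not discuss abrupt withdrawal.

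**Working it through.** There is no stated figure to reproduce. The check sets the provisions side by side and then does the dose and supply arithmetic.

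**1. Which provision reaches whom (active arm, from maintenance)**

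| Route off maintenance | Provision | Dose path in the text |
|---|---|---|
| Completes to Visit 4 | 5.2 scheduled taper | 120 → 60 (7 days) → 0 mg/day |
| Leaves the study while on drug | 4.4.5 decision with the cardiologist | taper or not, as decided |
| Stops under 5.3 and stays in | deviation record (5.3, 5.8) and ordinary adverse-event handling | 120 → 0 mg/day permitted |

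In 4.4.5, discontinuation means leaving the study. The section opens with participants who withdraw or are withdrawn, and it allows a referring practitioner to conduct the taper afterwards. In 5.3, the lower dose is offered as an alternative to taking none, not as a step required before it.

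**2. Dose**

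- Maintenance: 2 × 60 = 120 mg/day. Taper: 1 × 60 = 60 mg/day.
- Against the label's usual migraine range of 160 to 240 mg/day: 120/240 = 50% and 120/160 = 75%.
- A stop from titration goes from 60 to 0 mg/day, the same last step that completers take. It is not part of this point.

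**3. Supply needed for a 7-day step-down**

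- Capsules: 7 × 1 = 7.
- One planned four-week maintenance supply: 28 × 2 = 56 capsules, so 7/56 = 12.5%.
- The quantity actually dispensed is not stated. Assume that it follows the visit windows (Visit 2 on day 7 to 10, Visit 3 on day 28 to 42, Visit 4 on day 63 to 69):
  - Shortest interval: 28 − 10 = 18 days, 36 capsules, 7/36 = 19.4%.
  - Longest interval: 69 − 28 = 41 days, 82 capsules, 7/82 = 8.5%.
- Seven capsules equal 7/2 = 3.5 days of maintenance. Extra dispensing is needed only if the stop falls in the last 3.5 days of a supply.

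These figures measure the feasibility of the fix, not harm. The documents do not say how many participants would stop this way, and no number is assumed.

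**The case against.** The case against giving this much weight is substantial.

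- **The MOP may cover it.** How to take someone off drug is the kind of detail an overview leaves to such a manual. A reader might infer that the trial has no taper instruction. The documents do not support that; they show only that the protocol text has none.
- **5.3 orders no abrupt stop.** It fixes study status, and it names a lower dose first. With 60 mg capsules, the natural lower dose is 60 mg/day. The inference that 5.3 directs a one-step stop goes too far: it permits one.
- **The label is weaker here than it first appears.** Its firm advice on gradual reduction belongs to the angina warning, and coronary artery disease, clinically significant ECG abnormality and hyperthyroidism are excluded (4.2). What can reach this population is the suggestion of prudence where occult disease is possible and, by analogy, the suggestion of gradual withdrawal in migraine. Neither makes a taper mandatory.
- **4.4.5 has its own reason.** Participants who leave pass out of study care, so someone must settle their taper. Those who stop under 5.3 keep having vital signs, the Symptom Inventory and adverse-event review at each visit, with unscheduled visits available (6.6).
- **Other participants can stop abruptly too**, through non-adherence or loss to follow-up. For a missed visit, 4.4.4 says: "If a participant does not return for a scheduled visit, every effort should be made to contact the participant and document the outcome". That concerns contact, not dosing.

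Most of this stands and lowers the weight. Three things remain. Known coronary disease is excluded, but hypertension only if uncontrolled and smoking only from 25 cigarettes a day, with ages up to 65, so occult disease is possible. Visits 2 and 3, and Visits 3 and 4, are planned 28 days apart, and adverse events go to the site dentist or the cardiologist (8.1), so cardiologist input at the time of stopping is not assured. And this is the one abrupt stop that the protocol itself provides for.

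**Conclusion.** The gap holds on the protocol text: a participant may go from 120 to 0 mg/day under 5.3 and stay in the study, and neither the Visit 4 taper nor the 4.4.5 decision applies. It is a minor patient-safety point. The absolute risk is probably low, and the number affected is unknown.

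The endpoint, power and analysis are unaffected. Leaving maintenance is already a major deviation for the per-protocol sample, and the intention-to-treat sample keeps the participant's available assessments either way.

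The conclusion assumes that the MOP does not already give the instruction. If it does, only a cross-reference is missing. The case for acting rests on the low cost of the change, not on a large expected harm.

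**What to change.** Add to 5.3, or to the MOP with a cross-reference in 5.3:

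*A participant who stops study medication during maintenance but remains in the study will step down to one 60 mg capsule each evening for 7 days, as in the Visit 4 taper, unless the investigator, in consultation with the site cardiologist, judges that immediate cessation is needed (e.g., bradycardia, hypotension, bronchospasm, hypersensitivity).*

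- **Default.** Making the step-down the default matters, because a bare requirement to decide would leave the one-step stop as open as it is now. Seven days is shorter than the few or several weeks the label mentions; it is chosen to match what completers receive.
- **Blinding.** Apply the rule identically and blinded in both arms. This is workable because placebo is "dispensed, and administered in the same manner as described above for the active drug". Do not carry over the unblinding decision from 4.4.5; leave unblinding to 4.4.3.
- **Cost.** A few more cardiologist consultations, and a small amendment that needs IRB approval (14.1). The capsules and the site cardiologists are already in place.

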## **5.4 Placebo**

The placebo, which will be manufactured for this study, will be acquired, packaged, labeled, dispensed, and administered in the same manner as described above for the active drug.

---

Ingredients will be a microcrystalline cellulose filler and a gelatin capsule. Storage requirements for the placebo are the same as for the active drug.

## **5.5 Accountability Procedures**

The research pharmacies will be responsible for maintaining either paper or electronic logs for the acquisition and dispensing of the active drug and placebo. The pharmacies will also be responsible for maintaining and monitoring storage conditions for the active drug and placebo. The logs and records of storage conditions will be reviewed by the clinical monitor during periodic monitoring visits.

## **5.6 Assessment of Participant Compliance**

Participants will be asked to bring their medication containers to each visit during the treatment period. Study staff will count the number of capsules returned and will enter the number on a case report form in the EDC system. Participants will record the study medication use in the Daily Symptom Diary that will be reviewed by the study staff at Visits 2, 3, 4, and 5. Participant compliance with study medication will be defined as taking 60% or more of the study medication for the duration of the study.

## **5.7 Concomitant Medications and Therapies**

Prior and concomitant medication information will be collected for all participants for the 30 days prior to the Screening and Baseline Visit and during the study. Information collected will include medication, total daily dose, start date, stop date (if applicable), and primary reason for use. Information about treatment with injection therapy, acupuncture, biofeedback, TENS, and occlusal splint therapy will also be collected for all participants for the 30 days prior to the Screening and Baseline Visit and during the study.

### **5.7.1 Rescue Medication**

Rescue medications described below may be used to alleviate pain. Episodic use of a rescue medication will be defined as use for no more than 3 consecutive days and for no more than 18 total days from Visits 1 to 4.

#### **5.7.1.1 Over-the-counter medications**

NSAIDs are most often used to manage pain in TMD patients. If a participant is taking an over-the-counter medication daily for pain management, the participant will be encouraged to continue the same usage of that medication throughout the study. The usage of short-acting, non-prescription analgesics (e.g., NSAIDs, aspirin, and/or acetaminophen) by participants during the study will be recorded and quantified at each visit, and the usage will be classified as either daily or episodic.

---

#### **5.7.1.2 Prescription medications**

Participants who enter the study on a daily regimen of a prescription medication for pain will be encouraged to continue that regimen throughout the study. The usage of all prescription medications for pain during the study will be recorded and quantified at each visit.

#### **5.7.2 Nonpharmacological Therapy**

During the course of the trial, participants will not be restricted in the use of the nonpharmacological therapies, with the exception of acupuncture, biofeedback, and/or TENS. If, contrary to the study requirements, a participant starts acupuncture, biofeedback, and/or TENS treatment for the management of pain during the study, the use of these therapies will be recorded.

### **5.8 Protocol Deviations Related to the Use of Investigational Product and Concomitant Therapies**

The following protocol deviations related to the use of investigational product and concomitant therapies will be considered major protocol deviations and reported on a case report form in the EDC system.

- Participant is unable to reach the maintenance dosage of the study drug or placebo or is unable to remain on the maintenance dosage.
- Initiation of opioid medications.
- Initiation of TMJ surgical treatment (including TMJ arthrocentesis).
- Initiation of therapeutic injections for the management of pain.
- Initiation of occlusal splint therapy.
- Initiation of any of the following nonpharmacological therapies: acupuncture, biofeedback, and/or TENS.
- Initiation after Visit 1 and usage of short-acting, non-prescription analgesics (e.g., NSAIDs, aspirin, and/or acetaminophen) for pain that exceeds the definition of episodic use as described in Section 5.7.1.

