## 4 STUDY ENROLLMENT AND WITHDRAWAL

### 4.1 Participant Inclusion Criteria

A participant must meet all of the following inclusion criteria to be eligible for initial enrollment and randomization:

- 1) Provides a signed and dated informed consent form
- 2) Is between 18 and 65 years of age (inclusive; male or female and any race or ethnicity)
- 3) Meets diagnostic criteria for TMD, Group II: Masticatory Muscle Disorders, 1A: Myalgia
- 4) Has experienced facial pain for at least 3 months
- 5) Has experienced facial pain for at least 10 days of the last 30 days
- 6) At Screening and Baseline Visit (Visit 0), reports an average pain intensity rating over the past week of  $\geq 30$  on a numerical rating scale (0-100)
- 7) At randomization (Visit 1), has satisfactorily completed at least 4 entries per week in the Daily Symptom Diary within the preceding week and reported an average pain intensity score  $\geq 30$  on a numerical rating scale (0-100) or reports a rating of average daily pain intensity of  $\geq 30$  on the same scale on at least 3 days over the past week
- 8) If taking a prescription medication (with the exception of prescription formulations of NSAIDs, acetaminophen, and aspirin) episodically (or as needed) for the management of pain, agrees to discontinue its use prior to or at the Screening and Baseline Visit
- 9) If taking a prescription medication daily for the management of pain, agrees to continue the daily use of the medication throughout the study
- 10) If taking an over-the-counter pain medication daily, agrees to continue the daily use of the medication throughout the study
- 11) Agrees to not commence any new prescription medication for the management of pain throughout the study
- 12) Agrees to not commence any injection therapy for pain (e.g., tender or trigger point injections, steroid injections) during the course of the study
- 13) Agrees to not use acupuncture, biofeedback, or transcutaneous electrical nerve stimulation (TENS) for the management of pain during the course of the study
- 14) Agrees to not commence occlusal splint therapy during the course of the study
- 15) Agrees to continue use of splint therapy if commenced more than 30 days previously

---

- 16) Females agree to limit consumption of alcohol to no more than 7 drinks\* and males agree to limit consumption of alcohol to no more than 14 drinks\* a week for the duration of the study

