### 11.3.2 Per-Protocol Sample

Secondary statistical analysis of the primary hypothesis will be in the spirit of per-protocol analysis. The per-protocol sample will be a subset of the intention-to-treat sample, excluding any assessments made at or after a visit at which the participant is found to have any protocol deviation listed in Section 5.8. In addition, all assessments for participants whose compliance with study medication is less than 60% over all study visits will be excluded from per-protocol analyses.

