5.2 Protocol Deviations

The protocol deviations listed below are related to the use of investigational product and concomitant therapies and will be considered major protocol deviations. These deviations will exclude a participant's data from the PP analysis (Section 4.2).

Version 3.0 Page 9 of 25

- Participant is unable to reach the maintenance dosage of the study drug or placebo or is unable to remain on the maintenance dosage.
- Initiation of opioid medications.
- Initiation of TMJ surgical treatment (including TMJ arthrocentesis).
- Initiation of therapeutic injections for the management of pain.
- Initiation of occlusal appliance therapy.
- Initiation of any of the following non-pharmacological therapies: acupuncture, biofeedback, and/or TENS.
- Initiation after Visit 1 and usage between Visits 1 and 4 of short-acting, non-prescription analgesics (e.g., NSAIDs, aspirin, and/or acetaminophen) for pain that exceeds the definition of episodic use as described in Section 5.7.1 of the protocol.

These and other types of protocol deviations will be reported during the study. The types of protocol deviations will be summarized descriptively for both the Safety and ITT populations by treatment group. A listing of the protocol deviations of individual participants will be included in the participant listings.

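### The deviation list behind the per-protocol sample omits new non-opioid prescription analgesics, which Inclusion 11 forbids, and is ambiguous about escalated over-the-counter use

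*Protocol*

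**What the plan says.** At enrolment each participant accepts four bars on new pain treatment. The first, Inclusion 11 in Protocol 4.1, is: "Agrees to not commence any new prescription medication for the management of pain throughout the study". Inclusions 12 to 14 bar starting injection therapy, using acupuncture, biofeedback or TENS, and starting a splint.

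Protocol 5.8 lists seven major deviations, and SAP 5.2 repeats them in substance. Two concern analgesic drugs. One is "Initiation of opioid medications". The other is "Initiation after Visit 1 and usage of short-acting, non-prescription analgesics (e.g., NSAIDs, aspirin, and/or acetaminophen) for pain that exceeds the definition of episodic use". The SAP version adds a window: "Initiation after Visit 1 and usage between Visits 1 and 4 of short-acting, non-prescription analgesics". Protocol 5.7.1 defines episodic use as "use for no more than 3 consecutive days and for no more than 18 total days from Visits 1 to 4".

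The list determines the PP sample. Protocol 11.3.2 forms it by "excluding any assessments made at or after a visit at which the participant is found to have any protocol deviation listed in Section 5.8", and also drops participants with under 60% compliance. SAP 4.2 applies the same rule to the list in SAP 5.2, which says of the listed items: "These deviations will exclude a participant's data from the PP analysis". For prescription analgesics, Protocol 5.7.1.2 says only that "The usage of all prescription medications for pain during the study will be recorded and quantified at each visit". It attaches no consequence for the PP sample.

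**The concern.** The PP analysis is the only planned analysis of the primary endpoint that removes assessments because of competing analgesia. The ITT analysis keeps them on purpose (Protocol 11.3.1), and the rescue-medication models in SAP 8.3.2 analyse days of use without adjusting the pain index.

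SAP 8.3.1 also gives the PP result a job. If the primary result appears not to depend on the choice of population, all later analyses use ITT only. A PP sample that keeps assessments affected by unlisted analgesia is more like the ITT sample, so agreement between the two says less.

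The omission matters because the unlisted drugs are foreseeable. Protocol 2.1.2 names NSAIDs, antidepressants, anticonvulsants and muscle relaxants among the classes used for TMD pain, and Protocol 5.7.1.1 says NSAIDs are the most common choice.

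**Working it through.** The point rests on comparing texts. The documents state no figure to reproduce.

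**Step 1. Each bar at enrolment against the PP list.**

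| Bar (Protocol 4.1) | Item in Protocol 5.8 / SAP 5.2 |
|---|---|
| 11: new prescription pain medication, any class | opioids only |
| 12: injection therapy | listed |
| 13: acupuncture, biofeedback, TENS | listed |
| 14: occlusal splint | listed |

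The remaining items are failure to reach or hold the maintenance dosage, TMJ surgery, and non-prescription analgesics. None covers a non-opioid prescription drug.

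**Step 2. Is the gap closed elsewhere?** Protocol 14.12 makes any noncompliance a deviation, so breaking the Inclusion 11 commitment would be reported. But PP membership follows only from the list and the 60% compliance rule (Protocol 11.3.2, SAP 4.2). The summaries in SAP 5.2, 6 and 8.3.2 would describe such use without changing membership.

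**Step 3. Three cases under the plain reading.** The over-the-counter item joins two conditions: initiation after Visit 1, and use over the episodic limit.

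- A: no use before Visit 1, then an over-the-counter NSAID on 19 days between Visits 1 and 4. 19 > 18, and use began after Visit 1. Both conditions are met, so assessments at or after the visit where this is found are dropped.
- B: occasional use before Visit 1, then the same 19 days. Over the limit, but not initiated after Visit 1. Kept.
- C: a daily prescription NSAID newly started after Visit 1. It is against Inclusion 11, but is neither an opioid nor non-prescription. Kept.

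A and B have the same analgesic exposure on treatment and are treated differently. C took up a treatment it had agreed not to start and is kept.

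**Step 4. What the size would depend on.** Protocol 11.2 assumes net changes of -810 and -270, a difference of 810 - 270 = 540. Let p_P and p_D be the proportions of PP participants in the placebo and drug arms with unlisted analgesic use at Visit 4, and x the further fall in pain index it produces. Then

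observed difference = 540 - (p_P - p_D) × x.

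The documents give neither the proportions nor x. With assumed values, for illustration only:

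| p_P - p_D | x | Shift | Difference left | Shift / 540 |
|---|---|---|---|---|
| 0.05 | 300 | 15 | 525 | 2.8% |
| 0.10 | 600 | 60 | 480 | 11.1% |
| 0.20 | 900 | 180 | 360 | 33.3% |

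The last row is extreme: 900 points exceeds the whole 810-point change assumed for the propranolol arm. With equal use in both arms the shift is zero. With more use in the propranolol arm the difference widens.

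**The case against.** Which deviations count as major is partly the sponsor's choice, and the PP analysis is secondary. ITT is the default population (SAP 8.3), and the comparison in SAP 8.3.1 cannot change the primary result. Unequal analgesic use would also show in the concomitant-medication, rescue-medication and deviation summaries. All of this stands and limits the weight of the point. It does not explain why the breach of one commitment out of four is left off the list.

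The over-the-counter item can be read another way: as starting, after Visit 1, a level of use beyond episodic. On that reading case B is caught. The clause evidently means to spare participants already on a daily regimen, whom Inclusion 10 and Protocol 5.7.1.1 expect to continue. So this part is an ambiguity rather than a proven gap. But two programmers could build different PP samples from it.

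Removing assessments after analgesic use is not free of bias either. If the placebo participants removed are those doing worst, the difference can narrow. The change makes the PP sample consistent with the trial's own commitments; it does not make the PP estimate unbiased.

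A reader might infer more than the documents support:

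- That the list omits all new prescription pain medication. It does not; opioid initiation is listed.
- That the PP sample keeps the stronger analgesics. The documents give no ranking, and Protocol 2.1.2 calls evidence of efficacy in TMD scarce for all these classes.
- That a listed deviation removes the whole participant. SAP 5.2 alone could suggest this, but Protocol 11.3.2 and SAP 4.2 drop only assessments at or after the visit concerned.

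**Conclusion.** The concern holds in limited form. The lists in Protocol 5.8 and SAP 5.2 do not match Inclusion 11 for non-opioid prescription analgesics, and the over-the-counter item is ambiguous about participants who escalate earlier occasional use. Assessments affected by competing analgesia can therefore remain in the PP analysis of the primary endpoint, and the ITT/PP comparison is less informative for it.

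It would be tempting to conclude that the PP result is biased toward zero. The documents do not support that, because it requires more such use on placebo and no rates by arm are given. The illustrative shifts of 15 to 180 points rest wholly on assumed values. The primary ITT analysis is unaffected. This is a cheap improvement to a secondary analysis.

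**What to change.** Before unmasking, and for PP membership only, reconcile Protocol 5.8 and SAP 5.2 with Inclusion 11:

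1. Add starting any new prescription medicine taken for pain to the deviations that remove assessments at or after the visit where they are found.
2. Define the over-the-counter item as use between Visits 1 and 4 over the Section 5.7.1 episodic limit, except where a daily regimen already in place at Visit 1 is simply continued.

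One related case stays open under this wording. Inclusion 8 exempts as-needed prescription NSAIDs, acetaminophen and aspirin from discontinuation, and escalating one of these is neither new nor non-prescription. The same edit should state how it affects PP membership.

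The cost is two lines of text and a slightly smaller PP sample. Protocol 5.7 already collects drug, daily dose, start and stop dates and reason for use, so no new data are needed. What participants may take does not change.
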